### 3.10.2 Secondary Efficacy Analyses

#### 3.10.2.1 Durability of Response

Difference in time to recurrence of wart by treatment group is summarized using Kaplan Meier analysis. This analysis will be done at overall study level and by treatment cycle.

- **Overall Study Level:** Time to recurrence will be presented graphically with a Kaplan Meier curve. For this analysis, time to first recurrence in the study will only be included for each subject. Subjects with no wart at the end of study will be censored. The proportion of subjects that remain clear of warts at the end of the study will also be presented.
- **By Treatment Cycle:** For this analysis, time to first recurrence in the treatment cycle will only be included for each subject. Subjects with no wart at the end of the treatment cycle will be censored.

Kaplan-Meier estimates and associated confidence intervals are obtained using SAS statements consistent with the following syntax:

```
PROC LIFETEST ALPHA=.05;  
  TIME DAYS*CENSOR(1);  
  SURVIVAL OUT=SURV CONFTYPE=LOGLOG;  
  STRATA TREATMENT GROUP;
```

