14.3. Statistical Analysis of Efficacy

Unless otherwise stated, all efficacy summaries and analyses will be conducted using the ITT population. All efficacy summaries and analyses will be produced for the following groups:

- Subjects treated in the study that were randomized to active treatment during the previous A101-WART 301/302 study.
- Subjects treated in the study that were randomized to vehicle during the previous A101-WART 301/302 study.
- Subjects treated in the study overall.
- Subjects not requiring treatment during the study that were randomized to active treatment during the previous A101-WART 301/302 study.
- Subjects not requiring treatment during the study that were randomized to vehicle during the previous A101-WART 301/302 study.
- Subjects not requiring treatment in the study overall.
- All subjects combined

The primary efficacy analysis will be the effectiveness of A-101 45% based on the proportion of subjects who achieve complete clearance (PWA=0) of all identified common warts at any scheduled visit. Any identified common wart for a subject that has missing PWA data will be treated as not clear for the purpose of the primary efficacy analysis.

Four secondary efficacy analyses will be performed:

- Durability of response: for warts achieving a status of Clear (PWA=0), the number of weeks the wart remains clear will be tabulated and these results will be summarized using descriptive statistics. The proportion of these warts that remain clear at the end of the study will also be presented.
- Mean per-subject percent of treated warts that are Clear (PWA=0) at each visit will be summarized using descriptive statistics.
- Proportion of subjects with a single wart at baseline whose wart is Clear (PWA=0) will be summarized using descriptive statistics by visit.
- Median time to achieve onset of Clearance (PWA=0) for all treated warts.

Efficacy summaries will be supported by listings of PWA data.

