### 2. STUDY DESIGN

This is a Phase 3, open-label, long-term safety study of A-101 45% Topical Solution in subjects with common warts.

In order to be eligible for A-101-WART-303, subjects must have completed protocol treatment on either the A-101-WART-301 or A-101-WART-302 study.

Subjects that have complete clearance of all warts at the end of A-101-WART-301 or A-101-WART 302 may enter into the A-101-WART-303 study following completion of the Visit 1 assessments. These subjects will be followed every 6 weeks to assess for a recurrence or development of new common warts. If a recurrence occurs or a new wart develops these subjects may return to the investigational site to receive A-101 45% Topical Solution twice a week for an additional 8 weeks.

Subjects that have warts that have not cleared (or were not treated) at the completion of A-101WART-301 or A-101-WART-302 may enter into the A-101-WART-303 study following completion of the Visit 1 assessments will receive A-101 45% Topical Solution twice a week for 8 weeks.

Subjects may continue to receive A-101 45% Topical Solution twice a week for 8 weeks if their warts are not clear at the end of the 8-week treatment period but the 8 weekly treatments must be initiated by Day 122.

[figure not shown]
Visit 1 of A-101-WART-303 can be the same day as Visit 13 of either A-101-WART-301 or A101-WART-302.

All subjects will be required to remain on study for a total of 6 months.

During the study, the investigator may identify from 1 to 6 common warts to be treated twice a week for up to 8 weeks (maximum of 16 treatment applications). An 8-week treatment course may be repeated.

[Figure 1](#) below provides a graphical representation for treatment in this study.

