### 3.3 Study Day and Period Study Day

As shown in [Figure 1](#), subjects can potentially take multiple courses of treatment throughout the study. Subjects entering the study with warts will receive treatment at study entry as shown in [Table 2](#). Subjects who enter without any common warts do not receive study medication immediately and follow visit schedules shown in [Table 3](#). If these subjects develop any wart during the study, they will then begin a treatment regimen and follow the visit schedule for treated subjects. Subjects can initiate a treatment regimen up to three times (cycles) throughout the course of the study up to day 122. To allow for comparisons referencing each treatment cycle, Study Day will be calculated in two ways. Study day is defined as the relative day in the study from time of enrollment (first dose if treated immediately). Period study day is defined as the relative day from the day of first dose within a treatment cycle.

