### **3.10 Efficacy Endpoints**

The primary and secondary efficacy analyses will be carried out on the Safety Population. Efficacy summaries will be supported by listings.

Primary Efficacy Endpoint: Proportion of subjects who achieve complete clearance (PWA=0) of all identified warts at each analysis visit window by treatment group and treatment cycle.

Four secondary efficacy endpoints are:

- Durability of response: For subjects with all warts achieving a status of Clear (PWA=0), the number of weeks all warts remain clear by treatment group and treatment cycle.
- Mean per-subject percent of treated warts that are Clear (PWA=0) at each analysis visit by treatment group and treatment cycle.
- Proportion of subjects with a single wart at baseline whose wart is Clear (PWA=0) by analysis visit, treatment group, and treatment cycle.
- Median time to achieve onset of Clearance (PWA=0) for all treated warts by treatment group and treatment cycle.

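### As written, the overall durability rule censors anyone with no wart at study end, so a subject who recurred, was retreated and cleared again would lose a real recurrence

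*SAP*

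**What the plan says.** Duration of response is a named secondary objective in both documents. SAP 3.10 defines the endpoint for subjects whose warts have all cleared, as "the number of weeks all warts remain clear by treatment group and treatment cycle". For the overall Kaplan-Meier analysis, SAP 3.10.2.1 states that "time to first recurrence in the study will only be included for each subject", and the next sentence reads "Subjects with no wart at the end of study will be censored". The by-cycle bullet has parallel wording: "Subjects with no wart at the end of the treatment cycle will be censored". The sample SAS code sets event status through the statement beginning "TIME DAYS*CENSOR(1", so a record flagged 1 contributes no event. The same section also reports the proportion of subjects remaining clear at the end of the study.

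Protocol 14.3 describes the endpoint per wart: "for warts achieving a status of Clear (PWA=0), the number of weeks the wart remains clear will be tabulated". It gives no censoring rule, so it does not settle the matter.

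On retreatment, SAP 3.3 says "Subjects can initiate a treatment regimen up to three times (cycles) throughout the course of the study up to day 122". Protocol Table 2, footnote 6, allows drug to be dispensed at Visit 5 for a new cycle when warts have not cleared or new ones have appeared. Protocol 9.2 places the last PWA at Day 182.

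**The concern.** Two adjacent sentences fix event status in different ways. One looks at what happened first; the other looks at the subject's state on the last day. They agree unless a subject recurs and is clear again by the end, and in this study further active treatment can bring that about. In a time-to-first-event analysis, event status should not depend on a later state that retreatment can change.

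The error can run in one direction only. It removes recurrences and never adds them, and it removes those that occurred early enough to be retreated successfully. The better A-101 works on retreatment, the more durable the initial response would appear. The accompanying proportion remaining clear at study end could be read in the same two ways: continuously clear, or clear again.

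**Working it through.** **The plan's own figure.** The only figure that can be reproduced is the 148 in SAP 3.13: 200 × (1 − 0.26) = 148. It is correct but does not enter the durability analysis. Neither document gives a recurrence or re-clearance rate.

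**Is the path possible?** A cycle has its last application on cycle day 53 and a PWA at day 60 (Protocol Table 2). If it starts on Day 122, the last application falls on Day 122 + 53 − 1 = 174, and Day 182 is cycle day 182 − 122 + 1 = 61. So a subject can recur, complete a retreatment cycle and be assessed as clear at Day 182, meeting both the event definition and the censoring rule.

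SAP section 2 also says "If a recurrence occurs or a new wart develops these subjects may return to the investigational site to receive A-101 45% Topical Solution", but there 'these subjects' are those already clear when the parent study ended. For subjects who clear within this study, the path rests on SAP 3.3 and Protocol Table 2, footnote 6.

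**Size under stated assumptions.** Assume all warts clear at Day 60, a constant recurrence hazard to Day 182 (122 days), retreatment of every recurrence by Day 122 (62 days), and re-clearance c. Take c from 26% to 50%. The 26% is borrowed from SAP 3.13, where it is a per-wart figure for the parent studies; the 50% and the recurrence rate R have no source in the documents.

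- Hazard: h = −ln(1 − R)/122
- Share recurring by Day 122: E = 1 − exp(−62h)
- Understatement of recurrence, with the affected subjects censored at study end: E × c

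| R | E | Understatement, c = 26% | Understatement, c = 50% | Reported recurrence |
|---|---|---|---|---|
| 30% | 16.6% | 4.3 points | 8.3 points | 25.7% to 21.7% |
| 45% | 26.2% | 6.8 points | 13.1 points | 38.2% to 31.9% |

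**If only half of the early recurrences are found and retreated,** the 30% case halves: 16.6% × 0.5 × 0.26 = 2.2 points and 16.6% × 0.5 × 0.50 = 4.1 points.

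**If the latest start is Day 102.** SAP Table 3, footnote 2, gives Day 102 where SAP 3.3 gives Day 122; the two must be reconciled. With 42 days in place of 62, R = 30% gives E = 11.6% and an understatement of 3.0 to 5.8 points.

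**Kaplan-Meier illustration.** Take 100 hypothetical subjects clear at Day 60, with 20 recurring by Day 122 and 10 later. Censoring only those with no recurrence gives 70.0% recurrence-free at Day 182. Under the literal rule, suppose 2, 5 or 10 of the 20 clear again (10%, 26% and 50%, rounded to whole subjects):

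- Censored at study end: 1 − 28/100 = 72.0%, 1 − 25/100 = 75.0%, 1 − 20/100 = 80.0%.
- Time kept at first recurrence but flagged as censored: 71.6%, 74.0%, 78.3%.

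The recurrence is lost under either coding. This cohort places more recurrences before Day 122 (20 of 30) than the constant hazard does (16.6 of 30), so its differences are somewhat larger.

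**The case against.** The strongest reply is that the context shows the intent. The sentence just before makes first recurrence the datum for each subject, and SAP 3.10 counts the time all warts remain clear, a span that ends at recurrence whatever follows. On that reading the censoring sentence covers subjects who supplied no recurrence. The SAP also refers to a separate data-handling and programming specification (3.8 and 3.11), which is not available and may set the flag correctly. This stands as to intent. A reader might infer that the analysis will certainly score retreated subjects as never having recurred; the documents do not support that, because a programmer could resolve the conflict either way. The sentence as written still gives the wrong flag if followed.

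The by-cycle analysis is a partial safeguard. Retreatment normally opens a new cycle, so the recurrence should count against the preceding one. The SAP does not define when a cycle ends, so this is likely but not certain. A reader might infer that these recurrences disappear from the durability results altogether; that goes too far.

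Full detection is also optimistic. Protocol Table 2 schedules no office visit or PWA between Day 60 and Day 182. The one call in that interval before Day 122 is at Day 102 and asks about new warts, so finding a recurrence depends largely on self-report. This stands, and it makes the full-detection figures an upper limit for the assumed rates.

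Finally, the analysis is one of four descriptive secondary efficacy endpoints, with no formal test (SAP 3.10.1), in a study whose primary objective is safety. That limits the consequence but does not make the rule right.

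**Conclusion.** The point holds as a conflict between the written censoring rule and the event definition. Applied literally, the rule drops real recurrences from the overall analysis and can only overstate durability. The by-cycle analysis shares the wording and is less exposed.

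The size cannot be derived from the documents. With 30% true recurrence and 26% to 50% re-clearance, both assumed, reported recurrence is at most about 4 to 8 points low if every recurrence by Day 122 is found and retreated, and about 2 to 4 points low if half are. If the derived flag already follows the probable intent, the bias is nil. The larger figures at 45% recurrence show only how the result scales and should not be read as an expected bias. No hypothesis test is at risk, but duration of response is a stated objective and the correction is cheap, so it should be made.

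**What to change.** Replace the overall-level censoring sentence in SAP 3.10.2.1 with: *The event is the first recurrence after clearance of all warts, regardless of later retreatment or re-clearance; subjects with no recurrence are censored at their last wart assessment.* This also supplies a censoring date, which the SAP lacks, and covers subjects lost to follow-up while clear. Count a subject as remaining clear at study end only if there was no recurrence in between. Use the same event rule in the by-cycle analysis.

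Keep the SAP's subject-level definition. Whether a new wart counts as a recurrence is a separate question, and this change should not settle it by making the event site-specific.

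The cost is one SAP sentence, its by-cycle counterpart and the censoring flag in the derived dataset, with no new data collection. Durability may look less favourable than under the literal rule; if the flag was already going to be set by first recurrence, the overall curve does not change on this account.

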#### 3.10.2.2 Mean Per-Subject Percent Wart Cleared

Mean per-subject percent of treated warts that are Clear (PWA=0) at each analysis visit will be summarized descriptively by treatment group and treatment cycle. Subjects with non-missing PWA values are only included. For each subject, percent of cleared warts are computed before summarizing across subjects in a treatment group. Data from subjects who begin treatment later in the study will be included once they start treatment. Treatment cycle start date can vary from subject to subject.

### **3.10.2.3 Complete Clearance in Subjects With a Single Wart at Baseline**

Proportion of subjects with a single wart at baseline whose wart is Clear (PWA=0) will be summarized descriptively by treatment cycle, analysis visit, and treatment group.

Treatment cycle start date can vary from subject to subject. Subjects with a single Wart in the beginning of treatment cycle and without a Wart assessment at the timepoint analyzed are assigned non-clearance.

### **3.10.2.4 Time to Clearance of All Warts**

The last secondary endpoint analyzed, the difference in time to clearance of all warts from start of a treatment cycle between treatment groups, is summarized using Kaplan Meier analysis. Confidence intervals for clearance times are based upon the methods of Brookmeyer and Crowley. This analysis will be performed on a subject level by treatment cycle. Treatment cycle start date can vary from subject to subject. Subjects whose warts are not cleared at the end of a treatment cycle are censored.

Kaplan-Meier estimates and associated confidence intervals are obtained using SAS statements as shown in [Section 3.10.2.1](#).

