#### 3.2 Treatment Groups and Data Presentation

This is an open-label study with only one treatment arm. Subjects who enter the study with a common wart receive study medication immediately. Subjects who enter the study with no common warts do not receive study medication at the start and will not be treated at all if they do not develop any common warts throughout the course of the study. In order to be eligible for this study, subjects must have completed protocol treatment on either the A-101-WART-301 or A-101-WART-302 study. Both WART-301 and WART-302 were double-blind studies where subjects were treated with either active A-101 45% topical solution or vehicle solution. To best account for all potential exposure to A-101 45%, summaries and analyses will take into consideration both the current open-label treatment status as well as the randomized treatment assignment from the subject's respective double-blind study. This classification precipitates the following four treatment groups.

- Open Label A-101 45%: Double-Blind A-101 45%
- Open Label A-101 45%: Double-Blind Vehicle
- Open Label Not Treated: Double-Blind A-101 45%
- Open Label Not Treated: Double-Blind Vehicle

Depending upon analysis population, data will be summarized into all or a subset of treatment groups indicated above. Summaries on All Enrolled Population will display all four treatment groups. Summaries on Safety Population will display only first two treatment groups.

All data listings will be sorted by treatment group and subject ID. Subject ID will identify site number and double-blind study subject participated prior to open label study

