#### **3.10.1 Primary Efficacy Analysis - Complete Clearance of All Warts**

The primary efficacy summary will tabulate the number and percent of subjects achieve complete clearance (PWA=0) at each analysis visit by treatment group. This analysis will also be done by treatment group and treatment cycle. Treatment cycle start date can vary from subject to subject so analysis visits will be derived from period study day as

described in [Appendix A](#) and [Section 3.3](#). All efficacy analyses will be descriptive and there will be no formal statistical test to compare treatment groups.

Any identified common wart for a subject that has missing PWA data will be treated as not clear for the purpose of the primary efficacy analysis. A sensitivity analysis will be carried out using observed data.

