### **3.13 Sample Size**

The sample size is based on an estimate of how many subjects will be required to provide at least 100 subjects requiring repeated treatment for a wart over the course of the study.

- By recruiting 400 subjects, we estimate 200 subjects will have received active treatment in the A101-WART 301/302 studies.
- We expected approximately 26% of warts treated in A-101-WART-301/302 studies to be clear at the end of the A-101-WART-301/302 studies.
- Based on the assumption that 26% of warts will be clear, at least 148 subjects will require exposure to active treatment.
- We anticipate that some subjects originally randomized to vehicle (in double-blind studies) will be exposed to active treatment.

As a result, the study should exceed the target of exposing more than 100 subjects to repeated treatments over the course of the study.

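### The by-cycle difference in time to clearance between prior-A-101 and prior-vehicle subjects is confounded by parent-study selection and by A-101 course number

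*SAP*

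**What the plan says.** SAP 3.10.2.4 describes its endpoint as follows: "the difference in time to clearance of all warts from start of a treatment cycle between treatment groups, is summarized using Kaplan Meier analysis". It is analysed per subject and by treatment cycle. SAP 3.10.2.1 words durability the same way: "Difference in time to recurrence of wart by treatment group is summarized using Kaplan Meier analysis".

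Both analyses use the Safety Population, which holds only subjects who received study medication in 303. On it, SAP 3.2 says, "Summaries on Safety Population will display only first two treatment groups"; these are treated subjects with prior A-101 and treated subjects with prior vehicle. The cycle clock restarts in 303: "Period study day is defined as the relative day from the day of first dose within a treatment cycle" (SAP 3.3).

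SAP 3.10.1 limits the inference: "All efficacy analyses will be descriptive and there will be no formal statistical test to compare treatment groups".

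On numbers, SAP 3.13 says "By recruiting 400 subjects, we estimate 200 subjects will have received active treatment in the A101-WART 301/302 studies" and "Based on the assumption that 26% of warts will be clear, at least 148 subjects will require exposure to active treatment". For the other arm it says only "We anticipate that some subjects originally randomized to vehicle (in double-blind studies) will be exposed to active treatment".

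Protocol 14.3 asks for the median time to clearance and lists a pooled group of all subjects treated in 303. SAP 3.2 has no such group, and SAP 3.14 explains only the change of analysis population. The objectives name no comparison between groups.

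**The concern.** Everyone treated in 303 receives A-101, so a difference between the two columns invites the reader to see an effect of earlier A-101. Two features of the design stand in the way.

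- **Selection.** A subject who enters clear is treated only if a wart recurs or a new one appears. More subjects should enter clear after A-101 than after vehicle if A-101 works, so the prior-A-101 column is likely to be thinned more of subjects who respond easily.
- **Course number.** The parent-study course is not counted. At subject level, cycle 1 is at least a second A-101 course in one column and a first in the other. This offset needs no modelling assumption.

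The SAP neither aligns the columns on total A-101 courses nor cautions against reading them side by side. At stake is a misreading: slower or less frequent clearance in the prior-A-101 curve could be taken as loss of effect on re-treatment. Efficacy of further treatment and onset of action are both secondary objectives.

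**Working it through.** **1. The plan's own figure.** 200 prior-A-101 subjects × (1 − 0.26) = 148, as stated in SAP 3.13. So 200 × 0.26 = 52 start outside the treated set. The documents give no vehicle rate; at an assumed 5% to 15%, 10 to 30 of about 200 prior-vehicle subjects would do so.

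**2. Model.** The true effect of prior exposure is set to zero. Each subject has a clearance probability p per A-101 course, beta-distributed across subjects.

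- m = mean of p = 0.26 (SAP 3.13, stated for warts and applied there to subjects)
- ρ = correlation of a subject's outcomes across courses (assumed, 0 to 0.5)
- v = parent-study clearance on vehicle (assumed, 5% to 15%)
- r = share of subjects clear at entry who return for treatment (assumed, 0 to 1)

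Then E = E[p²] = m² + m(1 − m)ρ. A subject who did not clear on A-101 clears on the next course with probability m(1 − ρ); one who did clear, with probability m + (1 − m)ρ. Hence:

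- Prior A-101, cycle 1: [(1 − m)·m(1 − ρ) + r·m·(m + (1 − m)ρ)] / [(1 − m) + r·m]
- Prior vehicle, cycle 1: m if vehicle clearance is unrelated to p. If the chance of clearing on vehicle is (v/m)·p, it is [m − (v/m)E + r(v/m)E] / [(1 − v) + r·v].

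**3. Vehicle clearance unrelated to susceptibility (prior vehicle 26.0%).** Gap in percentage points:

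| ρ | r = 0 | r = 0.25 | r = 0.5 | r = 1 |
|---|---|---|---|---|
| 0 | 0 | 0 | 0 | 0 |
| 0.1 | 2.6 | 1.8 | 1.1 | 0 |
| 0.3 | 7.8 | 5.4 | 3.3 | 0 |
| 0.5 | 13.0 | 9.0 | 5.5 | 0 |

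Approximating the hazard ratio by log(1 − p_A)/log(1 − p_V), where p_A and p_V are the two cycle 1 clearance proportions, the r = 0 column runs from 1.00 (ρ = 0) through 0.67 (ρ = 0.3) to 0.46 (ρ = 0.5).

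**4. Vehicle clearers also the more susceptible subjects (r = 0).** Gap in percentage points:

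| ρ | v = 5% | v = 10% | v = 15% |
|---|---|---|---|
| 0.1 | 2.2 | 1.8 | 1.3 |
| 0.3 | 6.6 | 5.3 | 3.9 |
| 0.5 | 11.1 | 8.9 | 6.5 |

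**5. Worked case, ρ = 0.3, v = 10%.** E = 0.0676 + 0.26 × 0.74 × 0.3 = 0.1253, and (v/m)E = 0.0482.

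- r = 0: prior A-101 0.26 × 0.7 = 18.2%; prior vehicle (0.26 − 0.0482)/0.90 = 23.5%; gap 5.3.
- r = 0.25: (0.1347 + 0.065 × 0.482)/0.805 = 20.6%; (0.2118 + 0.0120)/0.925 = 24.2%; gap 3.6.
- r = 0.5: (0.1347 + 0.13 × 0.482)/0.87 = 22.7%; (0.2118 + 0.0241)/0.95 = 24.8%; gap 2.1.
- r = 1: 26.0% in both; gap 0.

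**6. Wart-level versus subject-level rate.** Clearing all of a subject's warts is harder than clearing one, so the subject-level rate may be below 26%. With an assumed 15%, v = 6%, ρ = 0.3 and r = 0: prior A-101 is 0.15 × 0.7 = 10.5%; E = 0.0225 + 0.03825 = 0.06075; prior vehicle is (0.15 − 0.4 × 0.06075)/0.94 = 13.4%; gap 2.9.

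**The case against.** The analysis is declared descriptive, with no test between groups. The primary objective is safety, and no decision hangs on the contrast. SAP 3.2 gives accounting for all A-101 exposure as the reason for the grouping, and Protocol 14.3 sets out the same split. Stratified Kaplan-Meier curves already give one estimate per group, and the labels show prior treatment. All of this stands, and it limits the point to interpretation.

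Four stronger readings are tempting but unsupported.

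- A reader might infer that the prior-A-101 column contains no parent-study responders. Cleared subjects with recurrent or new warts are treated and re-enter, subjects with previously untreated warts are included, and vehicle clearers drop out of their column too. The imbalance is one of degree.
- A reader might infer that any observed difference is created by selection. Selection is a sufficient possible cause, but its size rests on inputs the documents do not give, and a real effect of prior exposure could contribute.
- A reader might infer that the code will attach a p-value. The code stratifies by treatment group, but the SAP offers it only as indicative syntax and 3.10.1 rules out a formal test. Rejection rates for an unplanned test are therefore beside the point.
- A reader might carry the gap over to durability. The wording in 3.10.2.1 has the same weakness, but the calculation covers clearance only.

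**Conclusion.** The point holds as one of confounding. The by-cycle difference in SAP 3.10.2.4 compares groups formed partly by parent-study outcome and one A-101 course apart, so it does not estimate an effect of prior treatment. With no true effect, selection alone could give a cycle 1 gap of 0 to about 13 percentage points over ρ from 0 to 0.5 and r from 0 to 1. The gap is zero if susceptibility does not vary between subjects or if all cleared subjects return; a subject-level rate below 26% may make it smaller. No size is shown for time to recurrence. No sample size or alpha figure is wrong. It is a cheap improvement worth making, because neither a stated objective nor Protocol 14.3 asks for this difference.

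**What to change.** 1. In SAP 3.10.2.1 and 3.10.2.4, replace the between-group difference with separate Kaplan-Meier estimates for each group.
2. Restore the pooled group of all subjects treated in 303, as listed in Protocol 14.3.
3. Derive a subject-level cumulative A-101 course number (prior A-101: 303 cycle + 1; prior vehicle: 303 cycle) and tabulate clearance by it. Flag the reason for treatment: uncleared, recurrent, new or previously untreated wart. The flag is needed because for a new or untreated wart the 303 course is that wart's first, whatever the subject's count.
4. State that the groups are selected on parent-study outcome and that the contrast is not an effect of prior treatment.
5. Specify in the LIFETEST code that no group test is produced, so that the output agrees with 3.10.1.

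Setting prior-A-101 cycle 1 non-clearers from the parent study beside prior-vehicle cycle 2 subjects who did not clear in cycle 1 should be supportive only. That comparison is itself selected on taking a second course, and the spacing between courses differs.

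The cost is SAP wording, one derived variable, one flag and one code option, with no new data. The downside is a few more table columns and smaller cells by course number.
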